Form Section 5 - Research Plan

Complete this section in the order of all the following components: (A) Specific Aims, (B) Statement of Qualifications for Innovative Research Grant Award, (C) Background and Significance, (D) Previous and Current Studies, (E) Research Design and Methods, (F) Anticipated Results, (G) Human Subjects, (H) Gene Recombination, (I) Microbes in Risk Group 2, 3, 4, (J) Animal Investigations, (K) Potential Hazards, and (L) References. Please specify each item in separate paragraphs.

(A) Specific Aims

Overall aims: This project has two primary purposes. The first purpose is to develop a computerized adaptive knowledge and education system for testing and improving the patient's and caregiver's knowledge on both stroke and occupational therapy (OT). The second purpose is to develop a patient-centered, individual tailored OT program on the basis of the computerized adaptive knowledge and education system and examine its effect on ADL function in stroke patients.

Specific aims (as described according to the timeline of this project):

Phase 1 - First half year (0-0.5; 0.5 year):

1. To develop a 100-item pool for stroke and OT knowledge, respectively. All 200 items will be designed to be easy-to-understand for the patients and encompass the full spectrum of knowledge.
2. To develop educational materials using multimedia for stroke and OT knowledge. All the items of stroke and OT knowledge and their corresponding educational materials will be matched.

Phase 2 - Second half of the first year to the first half of the second year (0.5-1.5; 1 year):

1. To administer the 200 items on caregivers and patients with as wide a range of severity as possible. Because of the endurance/acceptability of patients, each patient will be interviewed with about 100 items randomly selected from the 200 items. Each caregiver will be interviewed for all 200 items. In addition, responses from 200 patients and 200 caregivers for each item are needed for data analysis. Thus, 400 patients and 200 caregivers will be interviewed.
2. To apply the educational materials for 100 patients and 100 caregivers. We will make sure that all the educational materials will be easy-to-understand for patients and caregivers.

Phase 3 - The second half of the second year (1.5-2; 0.5 year):

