The reasons for recruiting 400 patients are described as follows, although a theory-based mathematical function to calculate sample sizes needed for IRT is largely lacking.⁴⁸ First, because of the endurance/acceptability of patients, each patient will be administered about 100 knowledge items randomly selected from the 200 items and their corresponding educational materials. In addition, at least 200 responses for each item, or responses from 200 patients, are strongly recommended for data analysis.^{49, 50} Thus, about 400 patients will be interviewed.

To ensure selection of patients with a broad range of severity and days after stroke onset, we will use a stratified sampling method. Two stratifying variables will be considered. One is stroke severity (using the National Institutes of Health Stroke Scale [NIHSS]⁵¹ as 4 strata: mild [NIHSS 0-5], moderate [6-10], severe [11-20], and very severe [>20]). The other is time after stroke onset (3 strata: 0-3 months, 3-12 months, and > 12 months). We will determine whether the patients cover the entire spectrum of stroke severity and days after onset after one year of data collection. If not, we will later recruit patients who are less representative to ensure adequate representation of the stroke population.

Procedures:

All 200 items and their corresponding educational materials developed in Phase 1 will be coded and saved in personal computers (PC, a touchscreen notebook). We will randomly select items from the item pools to administer on each patient or caregiver. On average, each patient will be tested with about 100 items by face-to-face interview. After the testing, if a participant fails on some items, the corresponding educational materials will be presented. However, each session will be shorter than 1.5 hours to prevent patient/caregiver discomfort and fatigue. The patients/caregivers will be able to take a rest during the testing, if necessary. If a patient/caregiver cannot complete more than 60 items in one session, the patient will be invited to be tested again on another day, but within a week.

The data collection will be carried out by research assistants (full-time or part-time; occupational therapists or research nurses). All items will be administered by face-to-face interview. To avoid any possible interference during the interviews, all the interviews will be administered in a quiet room (e.g., individual treatment room or counseling room).

Data analysis

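### Phase 2: 400 patients give the stated minimum of 200 patient responses per item only on average, because each patient's items are drawn at random without described balancing

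*Protocol*

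**What the plan says.** Section (A), Specific Aims, Phase 2 sets a count per item, separately for patients and caregivers: "responses from 200 patients and 200 caregivers for each item are needed for data analysis". Because of patients' limited endurance, "each patient will be interviewed with about 100 items randomly selected from the 200 items". For caregivers, "Each caregiver will be interviewed for all 200 items".

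Section (E), Phase 2, Subjects repeats the reasoning. It concedes that there is little theory for sizing item response studies, then states that "at least 200 responses for each item, or responses from 200 patients, are strongly recommended for data analysis" and that "each patient will be administered about 100 knowledge items randomly selected from the 200 items". It concludes: "Thus, about 400 patients will be interviewed".

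Section (E), Phase 2, Procedures gives the selection rule: "We will randomly select items from the item pools to administer on each patient or caregiver". It adds: "On average, each patient will be tested with about 100 items by face-to-face interview". Sessions are kept under 1.5 hours, and a second session is offered only to participants who cannot complete more than 60 items. The one coverage check, after a year, concerns stroke severity and time since onset. Nothing is said about balancing or monitoring the number of responses per item.

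**The concern.** The requirement is worded as a minimum for every item, and it is the only numerical basis given for 400 patients. That number was reached by dividing total responses evenly over the items. An even division is what a balanced assignment produces, whereas independent random draws produce counts that scatter around the mean. Roughly half the items would then miss the stated minimum even if recruitment is full and every session is completed.

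These responses decide which items are kept and set the difficulty parameters of both adaptive tests in Phase 3, and the knowledge tests supply the Phase 4 outcome. Under the written rule, calibration precision differs between items by chance, although the same patients could supply near-equal counts. The point has to be settled before data collection, because no later analysis can supply responses that were not collected.

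**Working it through.** **Inputs** (sections (A) and (E), Phase 2): 400 patients; pool of 200 items; about 100 items per patient, so each item is included with probability 100 / 200 = 0.5; requirement of 200 patient responses per item.

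**The plan's own figure.** Patients = responses per item × pool size / items per patient = 200 × 200 / 100 = 400. This reproduces the stated number exactly. Equivalently, 400 × 100 = 40,000 responses over 200 items is a mean of 200 per item, with no margin.

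**Count for one item.** With exactly 100 items drawn independently for each patient, and all answered, an item's count is Binomial(400, 0.5):
- mean = 400 × 0.5 = 200; SD = √(400 × 0.5 × 0.5) = 10
- P(count below 200) = 0.480

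**Over the pool.**

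| Threshold | Expected number of items below it, of 200 |
|---|---|
| 200 | 200 × 0.480 = 96 |
| 195 | 58 |
| 190 | 29 |
| 180 | 4 |
| 175 | 1 |

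Simulating 1,000 data sets, with 100 of 200 items drawn without replacement for each of 400 patients, gave a mean of 96.1 items below 200 (95% range 88 to 104). The lowest count averaged about 173 (95% range 165 to 178).

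**Effect on precision**, taking the standard error as proportional to 1/√n:
- items below 200 have a mean count of about 191.7; √(200 / 191.7) = 1.02, so about 2% larger
- worst item: √(200 / 173) = 1.075, so about 8% larger

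**Sensitivity to the number of items per patient** (complete sessions):

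| Items per patient | Expected items below 200 |
|---|---|
| 95 | 166 |
| 98 | 127 |
| 100 | 96 |
| 102 | 65 |
| 105 | 29 |
| 110 | 4 |

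**Keeping unrestricted random draws.** About 434 patients give each single item a 95% chance of reaching 200. About 475 give a 95% chance that all 200 items do, treating items as independent.

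**Balanced allocation, 400 patients.** With complementary halves given to pairs and all items answered, every item has 400 / 2 = 200 responses. Two limits apply:
- Pairing strictly within the 4 × 3 = 12 severity-by-onset strata leaves one unpaired patient in each stratum with an odd count. If patients fall at random into 12 equal strata (an assumption), about 6 are unpaired, about 67 or 68 items stay below 200, and the lowest is about 197.
- If a small share of assigned items goes unanswered at random (an assumption; the protocol gives no rate), the expected numbers are:

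| Unanswered | Below 200: balanced / random | Below 190: balanced / random |
|---|---|---|
| 0.5% | 127 / 104 | 0 / 34 |
| 1% | 173 / 112 | 0 / 40 |
| 2% | 196 / 127 | 0.5 / 52 |

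Above roughly 0.35% unanswered, balancing leaves more items just under 200 than random draws do, but it still removes the large shortfalls.

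**The case against.** **The algorithm is not specified.** The protocol says items are selected at random, and a balanced split is also random. That is true. However, no balancing is mentioned in any of the three places that describe selection, so independent draws are the plain reading. If balancing is intended, one sentence settles it.

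**The inputs are approximate.** Both the number of items and the number of patients are given as approximate, and the sensitivity table shows how far the count of short items moves. This stands: 96 is the value at exactly 100 items, not a prediction. But the session limit and the repeat rule give no reason to expect an average above 100, and a lower average makes the shortfall worse.

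**The threshold is a rule of thumb.** No planned analysis has a cut-off at 200, and an item with 195 responses is calibrated in the same way as one with 200. This also stands, and it limits the consequence. The Methods call 200 strongly recommended; the Aims call it needed, and the sample was sized on it.

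**Caregivers might fill the gap.** A reader might infer this, since each caregiver answers all items. The Aims count patients and caregivers separately for each item, so they do not.

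**Half the bank is badly calibrated.** A reader might infer this from 96 of 200. The figures do not support it: typical short items miss by about eight responses, and random selection by itself introduces no bias into which responses are missing.

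**Conclusion.** The point holds as a modest design flaw. The minimum of 200 patient responses per item that justifies 400 patients is met only on average. About 96 of 200 items are expected below 200, about 29 below 190, and the lowest at about 173, assuming independent draws, exactly 100 items per patient, 400 patients and complete sessions. The standard error rises by about 2% for a typical short item and about 8% for the worst.

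It would be wrong to conclude that the item bank, or the knowledge scores built on it, are invalid. It would also be wrong to conclude that balancing guarantees 200 for every item: 400 leaves no margin for unanswered items, with or without balancing.

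The calculation uses the 200-item pool of the Aims and of Phase 2. Section (E), Phase 1 instead gives 200 items per pool and 400 in total. With 400 items and 100 per patient the mean would be 400 × 100 / 400 = 100, and every item would be expected to miss 200. That contradiction is separate and must be reconciled.

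**What to change.** In section (E), Phase 2, Procedures, replace unrestricted random selection for patients by balanced random allocation. For consecutive patients, split the pool at random into two complementary halves of 100, balanced by domain, and give one half to each. Match patients left unpaired within a stratum across strata. Alternatively, let the program favour the items with the fewest completed responses so far, which also corrects for unanswered items as data accrue.

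In the Aims and in Phase 2, Subjects, restate 200 responses per item as the target under complete sessions rather than as a guaranteed minimum.

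The cost is a small change to the item-selection code on the testing computers and a few sentences of text, made before data collection. No additional patients or testing time are needed.

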In addition, Rasch analysis yields a reliability coefficient, which is useful for determining the measurement precision of the measures. Furthermore, another structural equation model will be used to validate the stroke and OT knowledge measures. A CFA will be used to confirm the factor structure of the stroke and OT knowledge measures to establish its construct validity. The three indices (i.e., the RMSEA, CFI, and TLI) will be used to determine model data fit.⁵²⁻⁵⁴

To manage the possible missing data, we will first examine the patterns and frequency to determine why it is missing. If the data is missing systematically, we will exclude the data by "list-wise" deletion. For example, missing data on some particular items may be attributed to privacy issues. On the other hand, for data that is missing at random, we will use a multiple imputation method implemented in the software ConQuest to derive the estimated value of non-response items. These missing data management processes will also be applied on the remaining parts of this project.

Phase 3: Development of a personal computer version of the stroke and OT knowledge measures.

The stroke and OT knowledge measures (the personal computer version) will be developed and administered in 4 steps. First will be *item calibration*: The Rasch-calibrated item banks (every item with a specific "difficulty" parameter) will be used for developing the stroke and OT knowledge measures and the related simulations. Second will be *starting rule and initial function estimation*: We will use the maximum Fisher information (MFI) as the item selection algorithm, and the maximum a posterior (MAP) method to estimate the patient's ability (i.e., level of function or satisfaction). In administering the stroke and OT knowledge measures, the system will present an initial item with a moderate difficulty from the item banks for the participant. The participant's response to that item will give the CAT a basis for making the first tentative estimate of the tested participant's level of knowledge. Third will be *selecting further items*: The computer will select the item with the largest information gain for further testing; and

fourth, *stopping rule*: Excellent reliability (coefficient = 0.95) will serve as the stopping rule for both CATs.

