The patients and caregivers will be invited and will use the system individually. To determine effect on patients and caregivers, respectively, if a patient is recruited, we will not invite his/her caregiver, and vice versa. Both patients and caregivers will be randomly assigned into an experimental group (receiving the computerized knowledge and education system) or a control group (receiving additional rehabilitation) using numbers randomly generated by a computer. Allocation concealment will be applied. All the participants will be tested by the knowledge system at the beginning of the study, 4 weeks after inception of the study, and 3 months after inception of the study. All the testing will be administered by a research assistant who will be unaware of study-group assignment.

Regarding the sample size needed for this study, a difference of 20% on stroke and OT knowledge in favor of the experimental group will be expected. In addition, we expect that about 70% of the participants will complete all assessments. Therefore, about 25 patients and 25 caregivers will be required for each arm of the trial to achieve a sufficient statistical power of 80%.

Protocols for the experimental and control groups:

The patients/caregivers assigned to the experimental group will first receive the computerized adaptive knowledge testing system. They will be then given adaptive educational materials provided by the educational system according to their testing results. The participants will be instructed to read or

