100 sub-acute patients (including inpatients and outpatients) will be recruited from the National Taiwan University Hospital. The patients will meet the criteria (both inclusion and exclusion criteria) mentioned in the phase 4 study. Their caregivers will also be invited to participate.

Power analysis

A difference of 2 points (about 10%) on the Barthel index in favor of the experimental group will be regarded as clinically relevant.⁵⁷ In addition, we expect that about 70% of the participants will complete all assessments. Therefore, about 50 patients will be required for each arm of the trial to achieve a sufficient statistical power of 80%.

Procedure:

The patients will be randomly assigned into an experimental group (receiving the patient-centered program) or a control group (receiving additional rehabilitation). Allocation concealment will be applied. All participants will be assessed by trained raters at the beginning of the study, 4 weeks after inception of the study, 3 months after inception of the study, and 1 year after inception of the study. The raters will be unaware of study-group assignment. The cost of each group will be recorded.

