The participants in the control group will not be given the results of testing. However, oral explanations will be given by the research assistant if they have questions about the testing. These participants in the control group will be offered additional rehabilitation programs to serve as placebo. The time of the additional rehabilitation program will be similar to the time that the participants spend taking part in the experimental group, which we expect to be about 2 hours per week for 3 consecutive weeks.

Data analysis:

Baseline characteristics will be reported by descriptive statistics (e.g., mean and SD for continuous variables, or frequency tabulations for categorical variables) for each group. Homogeneity of both groups at the baseline (time 1) will be examined using a Student's t test or Mann-Whitney U test where appropriate. If there are between significant differences between both groups, statistical control (e.g., analysis of covariance, ANCOVA) will be applied for further analysis of effectiveness.

The primary analysis of effectiveness (full-analysis set) will consist of a comparison of the change scores between time 2 to time 1 and time 3 to time 2 in primary and secondary outcome measures. Analysis of variance (ANOVA) will be used to compare the change scores between groups. The analyses will be adjusted using ANCOVA for any significant differences at baseline. Intention-to-treat analysis will be applied. Alpha level will be set at 0.05. The statistical analyses will be done by use of SPSS (version 16.0).

Incremental cost-effectiveness ratios will be calculated as cost per QALY to assess the cost-effectiveness of the different programs.

(F) Anticipated Results

We expect that the patients and caregivers' original knowledge of stroke and OT would be limited or modest. Our adaptive knowledge and education system will efficiently improve their knowledge of stroke and OT. We anticipate that the CATs for stroke and OT knowledge can reach an overall reliability above 0.95 (i.e., excellent reliability) and require less than 10 minutes to administer or test fewer than 20 items to ensure its efficiency.

Furthermore, the patient-centered OT program using the adaptive knowledge and education system will improve ADL independence in stroke patients. The patient-centered OT program will be cost-effective in increasing ADL function and quality-adjusted life years.

Significance:

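### A missing-data rule written for item calibration is extended without limit and, as written, would delete randomised participants with systematically missing data from the Phase 4 and Phase 6 comparisons, against the stated intention-to-treat analysis

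*Protocol*

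**What the plan says.** The rule stands at the end of the Phase 2 data-analysis text, after the Rasch analysis. It has two branches.

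- Systematic missingness: "If the data is missing systematically, we will exclude the data by" list-wise deletion. The example given is that "missing data on some particular items may be attributed to privacy issues".
- Missing at random: "for data that is missing at random, we will use a multiple imputation method implemented in the software ConQuest", used to estimate values for unanswered items.

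The scope is then widened: "These missing data management processes will also be applied on the remaining parts of this project".

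The later parts include two randomised trials. In Phase 4 (Procedure), "Both patients and caregivers will be randomly assigned into an experimental group" or a control group. In Phase 6 (Procedure), "The patients will be randomly assigned into an experimental group (receiving the patient-centered program) or a control group". In both trials the Data analysis section names a full-analysis set, compares change from time 1 to 2 and from time 2 to 3 by ANOVA, and states "Intention-to-treat analysis will be applied". Both sample-size statements (Phase 4, Procedure; Phase 6, Power analysis) say "we expect that about 70% of the participants will complete all assessments". Neither trial section gives a missing-data rule of its own.

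**The concern.** Deleting incomplete records does least harm when the reason for the gap has nothing to do with the outcome. The protocol prescribes it for the opposite case, where a pattern behind the gaps has been recognised. In a calibration sample this costs some information about items. In a randomised comparison it removes people by a criterion judged after randomisation, so the groups compared may no longer be those that randomisation formed. That conflicts with the stated intention-to-treat analysis.

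The other branch does not fill the gap. Imputing unanswered items in an item-response program deals with a questionnaire that was partly completed. It does not deal with a visit that did not take place. A dropout therefore has either a deletion rule or no workable rule.

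The two arms make different demands. The experimental arm repeats testing and education until knowledge is judged satisfactory, while controls are not told their test results and receive extra rehabilitation. Missingness that differs by arm is therefore possible, although the protocol gives no dropout reasons and no dropout rate by arm.

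**Working it through.** **1. The plan's own figure.** Phase 6 asks for 50 patients per arm, for 2 Barthel points, 80% power and 70% completion. No SD is stated, so the figure cannot be reproduced from the document alone. Taking alpha 0.05 as two-sided (the side is not stated) and solving backwards gives an SD of about 2.98:

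n = 2 × (1.96 + 0.84)² × 2.98² / 2² ≈ 35 completers per arm, and 35 / 0.70 = 50.

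At that assumed SD, power is about 80% with 35 per arm and 92% with all 50. The planned size therefore already allows for the loss.

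**2. Upper bound on exposure.** The expected non-completion is 1 − 0.70 = 0.30.

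- Phase 4: 0.30 × 50 = 15 patients and 0.30 × 50 = 15 caregivers. Assessments are at baseline, 4 weeks and 3 months, the same three visits that enter the two change scores.
- Phase 6: 0.30 × 100 = 30 patients. Here the full set of assessments also includes the 1-year visit, which is outside the two change scores, so the number affected in the primary comparisons may be smaller.

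Both are ceilings for a second reason: only data judged systematically missing fall under deletion.

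**3. Bias from deletion.** Let m be the share lost in an arm and g the amount by which the mean change of those lost is worse than that of completers. The arm's full mean is the completers' mean minus m × g, so deletion overstates that arm by m × g. The error in the between-arm difference is

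bias = m(exp) × g(exp) − m(control) × g(control).

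Illustration on the Barthel scale, where the values of g are assumptions:

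- One arm only, m = 0.30, g = 2: 0.30 × 2 = 0.6 points, or 0.6 / 2 = 30% of the 2-point target.
- One arm only, g from 1 to 3: 0.3 to 0.9 points.
- Same m and same g in both arms: 0.6 − 0.6 = 0.

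**4. Simulation with no true effect.** 4,000 trials, 50 per arm, SD 2.98, about 30% missing per arm, incomplete cases deleted, two-sided t test at 0.05. Where missingness depended on outcome, it was driven by each person's deviation from the arm mean. SD and mechanisms are assumptions.

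| Missingness | Bias (points) | Type I error |
|---|---|---|
| Unrelated to outcome | −0.03 | 0.047 |
| Poor outcomes lost, same mechanism in both arms | 0.00 | 0.050 |
| Poor outcomes lost in experimental arm only | +0.75 | 0.185 |
| Poor outcomes lost in experimental arm, good ones in control arm | +1.53 | 0.61 |

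The harm depends on a difference between arms, not on missingness as such.

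**The case against.** The strongest reply is that the rule concerns items. Its example is item non-response, its imputation fills unanswered items, and it sits in a calibration analysis. The extension may have meant only unanswered items on later questionnaires. This is a fair account of the likely intent. It does not remove the problem, because the extending sentence carries no such limit and nothing later replaces the rule.

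A second reply is that handling of missed visits is often left to a statistical analysis plan, which is not at hand. Were the complaint that detail is absent, that would settle it. Here the protocol states a rule, extends it, and so sets it against its own analysis population.

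Four stronger readings are tempting, and the document does not support them.

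- That 30% of participants will be deleted. This is a ceiling, for the two reasons given in step 2.
- That observed 4-week and 3-month data are thrown away for anyone who misses a later visit. The protocol does not say whether deletion runs across all visits or within each change score. In Phase 4 it could not happen to 3-month data, since there is no later visit. In Phase 6 a patient who misses only the 1-year visit still has both change scores.
- That deletion must bias the result. With the same pattern in both arms the bias is about zero.
- That the trials lose their planned power. The sample size already allows for 70% completion.

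**Conclusion.** The concern stands in this form: a rule built for item non-response in calibration is applied without restriction to two randomised trials. Read as written, it would remove participants whose data are judged systematically missing, contrary to the stated full-analysis-set, intention-to-treat analysis. Its imputation branch does not reach missed visits.

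The exposure in step 2 is a ceiling. The size of any bias is unknown. The 0.6-point shift rests on three assumptions: the full 30% is lost, the losses differ from completers by 2 points, and this happens in one arm only. The Barthel scale is used because the Phase 6 power statement uses it. The outcomes listed as primary in Phase 6 (Frenchay index, Rasch-scaled comprehensive ADL score, adaptive ADL test) and the logit knowledge scores of Phase 4 have other units, so the figure does not carry over to them. The main harm is possible selection bias, not loss of power.

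**What to change.** 1. Limit the Phase 2 rule to item non-response in calibration (Phases 2 and 3), and withdraw the sentence that extends it to the rest of the project.
2. For Phases 4 and 6, state that no randomised participant is deleted because data are judged systematically missing. Analyse everyone with any follow-up, in the arm assigned, in a mixed model for repeated measures with arm, visit, arm by visit and the baseline score as covariate. The two planned comparisons can be taken from this model as contrasts. It uses partial follow-up and is valid under missing at random. Participants with no follow-up do not enter it, so report their number and reasons by arm.
3. Add a sensitivity analysis for data missing not at random that shifts the unobserved outcomes by arm. Set the shift on each outcome's own scale, for example as a fraction of its SD, because a single shift in points has no common meaning across these measures.

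Cost: one changed primary analysis and one extra sensitivity table. No new visits, data or participants are needed.
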